3.2 Exclusion Criteria

- Etiology for hydrocephalus other than idiopathic normal pressure hydrocephalus
- MMSE<14
- Patients who have Tinetti gait and balance scores of <18
- Kiefer Comorbidity index>5
- Patients not capable of providing an informed consent.
- History of intra-cerebral hemorrhage

6. Drugs/ Substances/ Devices

- a. The rationale for choosing the drug and dose or for choosing the device to be used.
 CSF diversion using shunt surgery is the standard of care treatment for the normal pressure hydrocephalus
- Justification and safety information if FDA approved drugs will be administered for non-FDA approved indications or if doses or routes of administration or participant populations are changed.

n/a

- c. Justification and safety information if non-FDA approved drugs without an IND will be administered.
- d. n/a

7. Study Statistics

a. Primary outcome variable.

The primary short term outcome variable will be the Tinetti gait and balance score, the MCV Gait Grade and the gait velocity defined as number of steps per second per 30 feet walk at 6 and 12 weeks after surgery.

The primary long term outcome variable will be the Tinetti gait and balance score, the MCV Gait Grade and the gait velocity defined as number of steps per second per 30 feet walk at 6 and 12 months after surgery.

b. Secondary outcome measures.

Secondary outcome measures include the - cognitive and incontinence measures, the Black Outcome Scale, the Marmarou Recovery Scale, the functional measures of the Barthel index,

Principal Investigator: [name]

Application Number: NA_00042178

SMAF Scale and Rankin Scale, Post-Surgery Questionnaire, Kudo iNPH grading scale, Kiefer Index and European NPH Scale.

Also, outcome measures at earlier time points (i.e., the first visit 2 weeks from surgery - and 6-week follow-up) will be examined as well as the slope of the change in the measures over the follow-up.

c. Statistical plan including sample size justification and interim data analysis.

General analytic method:

For each treatment order group, we will calculate the within patient paired differences of the 6 and 12 week follow-up measures. We will examine the distributions of these summary measures, and if not normally distributed, log transformation will be tried. If near normality cannot be achieved then non-parametric analyses will be used.

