Though we do not expect any carryover effects, we will first test for period effects and treatment-period interactions by testing whether the magnitudes of the mean period differences are unequal and whether the overall means for each treatment order group are different. General linear models will be used to assess treatment effect while accounting for within patient correlation. F-tests (or non-parametric Wilcoxon rank sum tests if normality cannot be achieved) will be used to test significance of treatment effects.

Specifically for the primary outcome:

We will calculate the within patient difference in the Tinetti gait score, the MCV Gait Grade and the gait velocity at 6 weeks (end of first treatment period) and at 12 weeks (end of second treatment period). This difference is the same as it would be if we calculated the change from baseline at each time period. General linear model analysis will be employed to test for period and treatment effects and the interaction, while accounting for within patient correlation. If there is no period effect, then the analysis can be simplified to reporting a paired t-test of the difference in the Tinetti gait score, the MCV Gait Grade and the gait velocity between the optimal and sub-suboptimal 6-week follow-up. If any patient is a treatment failure and is discontinued from a treatment arm, the measure at the time of failure will be carried forward to the 6-week measure.

Sample size calculation:

A mean difference in the Tinetti score of 5 points would be considered clinically meaningful. Given the inclusion criteria of a baseline Tinetti score of >18 and data from our clinic, we estimate the standard deviation for the change to be 5 points. Using a two-sided t-test with the Type I error level of 0.05, we will have 80% power to reject the null hypothesis of no difference when the total sample size of a 2x2 crossover design is 34. Adjusting for a dropout rate of 20% a sample size of 42 study subjects would be required.

Principal Investigator: [name]

Application Number: NA 00042178

1. Boon, A., et al. Dutch normal-pressure hydrocephalus study: prediction of outcome after shunting by resistance to outflow of cerebrospinal fluid. *J Neurosurg* **87**, 687-693 (1997).

- 2. McGirt, M., et al. Diagnosis, treatment, and analysis of long-term outcomes in idiopathic normal-pressure hydrocephalus. *Neurosurgery* **62 Suppl 2**, 670-677 (2008).

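### The primary comparison uses week-6/week-12 pairs and has no rule for patients with only a week-6 value; a mixed model on both values would be a cheap improvement

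*Combined protocol and SAP*

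**What the plan says.** Section 7c, under the general analytic method, states for each treatment order that "we will calculate the within patient paired differences of the 6 and 12 week follow-up measures". The paragraph on the primary outcome repeats this: "We will calculate the within patient difference in the Tinetti gait score, the MCV Gait Grade and the gait velocity at 6 weeks" and at the end of the second period, 12 weeks.

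A general linear model for period, treatment and their interaction follows, allowing for correlation within patients. If there is no period effect, the plan may report a paired t-test instead.

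The only rule for an incomplete period concerns treatment failures, whose value at failure is carried forward to that arm's 6-week measure. Section 4f keeps failures in follow-up, so they are not dropouts. It also rules out sub-optimal drainage for them from then on.

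The sample size paragraph ends: "Adjusting for a dropout rate of 20% a sample size of 42 study subjects would be required". It does not say when the dropouts are expected to leave. Section 7c gives no missing-data assumption and no sensitivity analysis for dropout.

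**The concern.** A within-patient difference exists only when both values exist. A patient measured at week 6 who then leaves has a randomised, blinded first-period result, and neither the differences nor the paired t-test can use it.

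Discarding these patients is harmless if leaving is unrelated to outcome. In this design it may not be. At week 6 one sequence has drainage impeded and the other has it opened, so the reasons to stay can differ by sequence. The clinicians who make safety decisions know the valve status and see the gait scores. If the patients who remain are selected differently in the two sequences, the estimated drainage effect shifts. The analyst would also be left to decide, after the data are in, whether one-period patients count.

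**Working it through.** **1. The plan's own figures.** Inputs from the sample size paragraph of section 7c: a target difference of 5 Tinetti points; for the spread, "we estimate the standard deviation for the change to be 5 points"; alpha 0.05, two-sided; power 80%; 34 evaluable patients in all.

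- A two-sample t-test with difference 5 and SD 5 needs 17 per group, 34 in total, at 80.7% power. The 34 reproduces.
- 34 / 0.8 = 42.5, stated as 42.
- 42 × 0.8 = 33.6 remain and 42 × 0.2 = 8.4 are lost. Power is 79.5% with 33 and 80.7% with 34, so the loss of numbers is already budgeted.
- The 8.4 is an upper bound on patients with week 6 only, because it puts every dropout after week 6.

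**2. When complete pairs are biased.** Let δA and δB be the amounts by which the mean week-6 score of those who stay departs from that of all randomised patients, in the draining-first (A) and non-draining-first (B) sequences. Let ρ be the correlation between the two visits, with equal SDs. The stayers' week-12 mean shifts by ρδ, so their week-6 minus week-12 difference shifts by (1 − ρ)δ. The crossover estimate is half the difference between the sequence means, (dA − dB)/2. Hence

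bias = (1 − ρ)(δA − δB)/2.

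- Equal selection in both sequences (δA = δB) gives no bias. A simulation with the same score-dependent loss in both sequences and no true effect gave 0.00 within simulation error.
- If good draining-first scorers leave, δA is negative and the estimate is too low. If poor ones leave, it is too high.
- The bias shrinks as ρ rises.

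**3. Size.** The following are assumptions, not in the documents: SD 5 per visit, ρ from 0.3 to 0.7, logit slope of leaving 1 to 2 per SD of the week-6 score, and about 20% leaving, all after week 6. At ρ = 0.5, SD 5 per visit gives an SD of the difference of 5 × √(2 × 0.5) = 5. The true effect is 5. Complete-pair estimates at slope 1 / slope 2:

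| Who leaves | ρ = 0.3 | ρ = 0.5 | ρ = 0.7 |
|---|---|---|---|
| Good draining-first scorers; others at random | 4.71 / 4.52 | 4.77 / 4.66 | 4.87 / 4.80 |
| Good draining-first and poor non-draining-first scorers | 4.41 / 4.11 | 4.60 / 4.37 | 4.74 / 4.62 |

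- Row 1 is a bias of 5 − 4.87 = 0.13 to 5 − 4.52 = 0.48. Row 2 is 5 − 4.74 = 0.26 to 5 − 4.11 = 0.89.
- Check on row 1, slope 2, using the formula. At ρ = 0.5, −0.34 = 0.5 × δA/2, so δA = −1.36. Then ρ = 0.3 gives 5 − 0.35 × 1.36 = 4.52 and ρ = 0.7 gives 5 − 0.15 × 1.36 = 4.80, as simulated.
- If poor draining-first scorers leave instead (ρ = 0.5), the estimates are 5.22 / 5.32. With no true effect, slope 2 gives a spurious +0.34.
- If only 10% leave after week 6 (row 1, ρ = 0.5), the estimates are 4.88 / 4.82.
- Random leaving gives 5.00. The SE is 0.87 for complete pairs and 0.84 for a likelihood-type fit to all available values (ρ = 0.5).

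The all-available fit gave about 5.0 in every scenario with a true effect of 5. That is expected, because leaving was simulated to depend only on the observed week-6 value.

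**4. Draining-first failures.** Under section 4f such a patient never has a sub-optimal value. The carry-forward rule fills only the arm in which the failure occurred. The later values are under drainage, and section 7c does not say how they enter the comparison. The protocol itself therefore creates an outcome-dependent loss in one sequence.

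**The case against.** The strongest reply is that the plan may already do what is asked. Section 7c describes the paired differences as summaries whose distributions will be examined. The stated test is a general linear model that allows for within-patient correlation. With a single difference per patient no such correlation would remain, so the wording points towards modelling both values. This stands in part: a mixed model would keep one-period patients and a fixed-patient fit would drop them, and the plan does not say which is meant.

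Further points that stand:

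- Patients are blinded, and both sequences have a valve change and X-ray at week 6. Nothing in the documents shows that leaving will differ by sequence, or how strongly.
- The worst non-draining-first patients are handled as failures: they stay in follow-up and have a carry-forward value. Only poor scorers short of failure could follow the second row of the table.
- The biases are small against a 5-point target and an SE of 0.87.

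A reader might infer that dropouts certainly contribute nothing. That is certain only for the differences and the paired t-test. A reader might also infer that any dependence of leaving on the week-6 score biases the effect, or always understates it. Step 2 shows that selection must differ between sequences and that the sign can go either way.

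**Conclusion.** The point holds as a cheap improvement. The differences and the paired t-test exclude patients with week 6 only, the model sentence leaves their status open, and no rule covers them. Up to about 8 of 42 patients are concerned.

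If selection differs by sequence, the bias is about 0.1 to 0.5 points of a true 5 when only draining-first leaving depends on the score, and up to about 0.9 when leaving in both sequences does. These figures rest on the assumed SD, correlation, slopes and timing of dropout.

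The documents do not support reading this as a loss of power, since 42 already allows for it. Nor do they support reading it as a demonstrated bias. The gain in precision is small; the gain is protection against selective leaving and a model fixed in advance.

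**What to change.** In section 7c:

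1. Replace the analysis of differences and the paired t-test with a linear mixed model on the week-6 and week-12 values, with fixed treatment and period and a random patient effect. Include every randomised patient with at least one of the two values.
2. State the assumption that data are missing at random given the observed values.
3. State how draining-first failures, who have no sub-optimal value, enter the analysis.
4. Keep the complete-pair analysis as a sensitivity analysis, and say whether the log-transform and non-parametric fallback still applies.

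With complete data from both sequences, the model gives the same treatment estimate as the period-adjusted crossover difference analysis. The cost is wording and a standard procedure; no new data or patients are needed. The downside is reliance on missing at random, which is a weaker assumption than the one complete pairs require.

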treatment failure as this is considered under standard of care to be high risk of fall.
Additionally any patient falling due to inability to balance or poor gait would also be
considered a treatment failure.

Any patient deteriorating to failure level or having a fall attributable to gait impairment will be recorded as a treatment failure for that arm of the study and if on suboptimal drainage arm will be crossed over to optimal drainage level.

Patients who fail would however continue to participate in study and data will be collected at all subsequent follow-up points regardless of the study arm as described above. Furthermore, for concerns of patient safety no patient who fails (Tinetti \leq 18) will subsequently have suboptimal drainage in shunt at anytime^{12,13}.

Response:

Gait

- Tinetti gait and balance scale: Measured with respect to baseline (pre-drainage trial scores)
- 2. TUG: Measured with respect to baseline (pre-drainage trial scores)
- 3. MCV Gait Grade: Measured with respect to baseline (pre-drainage trial scores)

Cognition

- 1. Mini Mental State Examination (MMSE)
- 2. Rey Auditory Verbal Learning Test (RAVLT): Measured with respect to baseline (pre-drainage trial scores)
- 3. Trail Making Test A & B: Measured with respect to baseline (pre-drainage trial scores)
- 4. Writing the Alphabet: Measured with respect to baseline (pre-drainage trial scores)
- 5. Beck Depression Inventory

Principal Investigator: [name]

Application Number: NA 00042178

- 6. Stroop test
- 7. Pegboard

Urinary

- 1. Urinary Incontinence Questionnaire (ICIq-UI): Measured with respect to baseline (predrainage trial scores)
- 2. Overactive Bladder Questionnaire (ICIq-OAB): Measured with respect to baseline (predrainage trial scores)
- 3. Quality-of-Life related to lower urinary tract symptoms (**ICIq-LUTSqol**): Measured with respect to baseline (pre-drainage trial scores)
- 4. Global quality-of-life assessment (**AUASSqol**): Measured with respect to baseline (predrainage trial scores)
- 5. Voiding Diary

Functional Scales

- 1. Barthel Index: measured with respect to baseline (pre-drainage trial scores)
- 2. Modified Rankin Scale
- g. Description of what happens to participants receiving therapy when study ends or if a participant's participation in the study ends prematurely.
- Inclusion/Exclusion Criteria3.1 Inclusion Criteria

 - Age of Patients (between 55 to 85 years old)
 - Clinically suspected iNPH with at least gait impairment.

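### Section 7c names no baseline covariate for the order-group (carryover) test or for any 2- or 6-week comparison between orders; adding one is a minor, nearly free gain in precision

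*Combined protocol and SAP*

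**What the plan says.** Section 7c (primary outcome) takes the within-patient difference between week 6 and week 12 for Tinetti, MCV Gait Grade and gait velocity, and adds: "This difference is the same as it would be if we calculated the change from baseline at each time period". The model is then described: "General linear model analysis will be employed to test for period and treatment effects and the interaction, while accounting for within patient correlation". No baseline term is mentioned.

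Section 7c (general analytic method) says that, although carryover is not expected, a first step will test period effects and treatment-period interaction, the latter by asking "whether the overall means for each treatment order group are different". Section 4a justifies the absence of a washout by the belief that any carryover is short.

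Section 7b lists, among secondary outcomes, "outcome measures at earlier time points (i.e., the first visit 2 weeks from surgery" and the 6-week follow-up. It says these will be looked at, together with the slope of change, and names no model or between-order test.

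Section 4f (Response) gives "Tinetti gait and balance scale: Measured with respect to baseline (pre-drainage trial scores", and says the same of TUG, MCV Gait Grade and most of the listed cognitive, urinary and functional measures. Gait velocity, one of the three primary variables in 7a, is not in that list.

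The sample-size paragraph states: "A mean difference in the Tinetti score of 5 points would be considered clinically meaningful". It takes an SD of 5 for the change, without saying which change, and claims "80% power to reject the null hypothesis of no difference when the total sample size of a 2x2 crossover design is 34".

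**The concern.** A pre-drainage score exists for Tinetti (an entry criterion) and for MCV Gait Grade and TUG, all recorded before drainage is allocated. Subtracting baseline makes no difference to a within-patient contrast. It does matter when one group of patients is compared with another, because the stable differences between patients then stay in the error term.

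Two comparisons are of that kind. The test of order-group means is one, and it is planned explicitly. Any drainage comparison at 2 or 6 weeks would be another, since patients are still in their first period. With about 17 patients per order, a chance baseline imbalance could be mistaken for carryover or for an early drainage effect. Both comparisons would also be less precise than the collected data allow. At stake is the quality of the carryover check and of the first-period estimates, not the primary result.

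**Working it through.** **Inputs.** From section 7c: difference 5, SD of change 5, two-sided 0.05, 34 patients. Allocation is 1:1 (section 4a), so 17 per order. Not in the documents and therefore assumed: the correlation r, taken as equal between baseline B, week 6 (Y6) and week 12 (Y12), with a common variance s².

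**The plan's own figure.** In a two-sample t-test with 17 per order, the standard error is 5·√(2/17) = 1.715 and the noncentrality 5/1.715 = 2.92. With 32 degrees of freedom, power is 80.7% (16 per order gives 78.1%). So 34 reproduces as a two-group calculation. Below, the SD of 5 is read as the SD of change from baseline, so s = 5/√(2(1−r)).

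**Primary contrast.** (Y6−B) − (Y12−B) = Y6 − Y12 exactly. In a simulation (4,000 trials, r = 0.6, raw SD 5, 34 patients) the standard error of the treatment effect was 0.77 without and 0.78 with the covariate: no gain.

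**Week-6 comparison between orders.** The SD that enters the test is:
- raw score: s
- change score: 5
- baseline as covariate: s·√(1−r²) = 5·√((1+r)/2), with 31 degrees of freedom. At r = 0.5 this is 5·√0.75 = 4.33.

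The same formulas apply at week 2 if the SD and r are the same there.

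**Order-group means.** Let M = (Y6+Y12)/2. Its variance is:
- raw: s²(1+r)/2
- change, M−B: s²·3(1−r)/2 = 18.75 at every r
- covariate: s²((1+r)/2 − r²) = 25(1+2r)/4

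The covariate/change ratio of standard errors is therefore √((1+2r)/3), for example √(2/3) = 0.816 at r = 0.5. The difference tested is illustrative. Carryover enters only the second period, so a 5-point differential carryover shifts the patient mean by 5/2 = 2.5.

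| r | Week 6, 5 points: raw / change / covariate | Order means, 2.5 points: raw / change / covariate | Fall in order-mean SE with covariate: vs change / vs raw |
|---|---|---|---|
| 0.3 | 91.7 / 80.7 / 93.8% | 54.6 / 37.2 / 60.8% | 27% / 7% |
| 0.5 | 80.7 / 80.7 / 90.3% | 37.2 / 37.2 / 51.5% | 18% / 18% |
| 0.7 | 59.1 / 80.7 / 86.5% | 22.1 / 37.2 / 44.6% | 11% / 35% |
| 0.8 | 43.2 / 80.7 / 84.5% | 15.6 / 37.2 / 41.8% | 7% / 46% |

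The last column ignores the one lost degree of freedom. For a 1.25-point difference in order means, change-score power is 12.9%; the covariate gives 17.0% at r = 0.5 and 14.9% at r = 0.7.

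**Simulation check** (same settings as above), standard errors for raw / change / covariate: order means 1.55 / 1.34 / 1.17; week 6 1.71 / 1.54 / 1.39. The ordering agrees with the formulas.

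**The case against.** Several objections stand in whole or in part.

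- **The sentence on change from baseline is right.** A reader might infer that the plan makes an error there, or drops baseline because it cancels. The text supports neither: the sentence refers only to the within-patient difference, and no reason for the absent covariate is given.
- **Section 7b names no test.** A reader might take the 2- and 6-week outcomes as planned drainage comparisons. The section says only that they will be looked at. The point therefore applies to them only if such a comparison is made; the order-group test is the explicit case. Week 6 is also not cleanly first-period for everyone, because failures during suboptimal drainage are switched early and their failure value is carried forward.
- **Section 4f already refers to baseline.** If change scores are what is tested, baseline is used, only less efficiently. The largest gains, 90.3 − 80.7 = 9.6 to 86.5 − 59.1 = 27.4 points at week 6 and 44.6 − 22.1 = 22.5 points for order means at r = 0.7, need raw scores as comparator. That is the least favourable reading, and 7c does not settle which form is meant.
- **r is unknown.** The Tinetti entry threshold restricts the range and may lower r. At r = 0.3 the week-6 gain over raw scores is only about 2 points. At that same r, however, change scores do clearly worse than raw scores, whereas the covariate does best at every r in the table.
- **Nothing in 7c depends on the result.** No consequence is attached to a significant order-group difference. This limits the importance of the point but does not remove it.

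**Conclusion.** The point holds as a minor precision improvement outside the primary contrast. The order-group test is planned between patients with no baseline term, and the score that would sharpen it is already collected.

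Against change scores, the gain at week 6 is 9.6, 5.8 and 3.8 percentage points of power at r = 0.5, 0.7 and 0.8. For a 2.5-point difference in order means it is 14.3, 7.4 and 4.6 points. Against raw scores the gains are larger once r exceeds 0.5. These figures rest on an assumed r, equal correlations and variances, an SD of 5 read as change from baseline, and an illustrative carryover difference that the documents do not give.

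Two stronger conclusions might be drawn and are not supported. First, the primary analysis and the sample size are not weakened: with complete data the within-patient contrast gains nothing from baseline. Second, the covariate does not make the carryover test adequate. Power remains well below 80% in every case computed, so a non-significant result would still not establish absence of carryover.

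**What to change.** Add to section 7c that the comparison of order-group means, and any between-order comparison at 2 or 6 weeks, will use a linear model with treatment order and that measure's pre-drainage score as covariate. Apply this to measures with a recorded baseline: Tinetti, MCV Gait Grade, TUG and the secondary scales listed with one. Include gait velocity only if a pre-drainage value is recorded. Name a rank-based version of the same adjusted comparison for use if normality fails, in line with the plan's existing non-parametric fallback.

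Leave the sentence on change from baseline, the within-patient primary contrast and the sample size unchanged. It would help to add that a non-significant order-group test will not be read as evidence of no carryover.

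The cost is a short addition to the text and one degree of freedom per model, with no extra patients or visits. Fixing the form in advance also removes a later choice among raw, change and adjusted analyses.

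### A test for a period effect may decide whether the primary analysis adjusts for period; if the sequences end unequal, this biases the treatment estimate slightly and raises the type I error to about 6% at worst under the planned numbers

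*Combined protocol and SAP*

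**What the plan says.** Section 7c sets the order of testing: "we will first test for period effects and treatment-period interactions". For the primary outcome it repeats that "General linear model analysis will be employed to test for period and treatment effects and the interaction", allowing for correlation within patients. It then permits a change of analysis: "If there is no period effect, then the analysis can be simplified to reporting a paired t-test" of optimal against suboptimal drainage. It gives no criterion or significance level for deciding that there is no period effect.

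The sample size paragraph in the same section gives the planning values: "A mean difference in the Tinetti score of 5 points would be considered clinically meaningful", "we estimate the standard deviation for the change to be 5 points", and "80% power to reject the null hypothesis of no difference when the total sample size of a 2x2 crossover design is 34". It raises 34 to 42 for 20% dropout. Section 4a sets 1:1 allocation to the two sequences and does not describe how the list is generated.

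Section 4f, on treatment failure, states that no patient who fails "will subsequently have suboptimal drainage in shunt at anytime". Section 7c carries the value at failure forward to the 6-week measure of that arm.

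**The concern.** The period test here selects the reported analysis. A period effect that is present but missed is left out of the model, and the paired t-test then treats it as zero.

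A period effect is plausible. Period 1 begins at shunt surgery and includes recovery from it, while period 2 has no operation and comes after repeated testing. Whether it is still material at the 6- and 12-week endpoints cannot be settled from the documents.

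Unequal sequences are possible. Dropout of 20% is planned. The failure rule also acts differently by sequence: a patient who fails on optimal drainage in period 1 can never supply a suboptimal period, whereas a patient who fails on suboptimal drainage in period 1 crosses over and can supply both measures.

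At stake are the size of the primary treatment estimate, its 5% level and its confidence interval. If optimal-first patients are lost more often and period 2 scores are higher, the bias favours the shunt. If only one of these is reversed, it goes the other way.

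**Working it through.** **Inputs from section 7c:** difference 5 points; SD 5 points; two-sided 0.05; 34 evaluable and 42 enrolled. **From section 4a:** 1:1 allocation, so 21/21 if 42 are enrolled. **Assumed, because the documents do not say:** a period effect of 2 points (1 to 4 also run), a period test at two-sided 0.05, and loss unrelated to outcome.

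**Step 1: the plan's own figure.** A two-sample t-test with difference 5 and SD 5 has standard error 5 × √(2/17) = 1.715 with 17 per group, and power 80.7%. So 34 reproduces. In a crossover the standard error is (s/2) × √(1/n1 + 1/n2), where s is the SD of the within-patient difference. At 17/17 this equals 1.715 when s = 10. The text does not say which SD the 5 is, so s = 5, 7.07 and 10 were all run.

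**Step 2: bias of the paired estimate.** Let τ be the treatment effect and π the period effect (period 2 minus period 1). The optimal minus suboptimal difference has mean τ − π in the n1 optimal-first patients and τ + π in the n2 suboptimal-first patients. The pooled mean is therefore τ − π(n1 − n2)/(n1 + n2). The period-adjusted estimate, half the difference between the two sequences' mean period differences, has mean τ.
- 17/17: bias 0.
- 19/15: 2 × 4/34 = 0.24 point in size.
- 21/13: 2 × 8/34 = 0.47 point in size.

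These apply when the paired t-test is the analysis reported. Averaged over both branches of the rule, the bias is smaller.

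**Step 3: which splits the plan allows.** 42 − 34 = 8 losses. From 21/21 the most extreme split is 21/13. If loss is unrelated to sequence, all 8 fall in one sequence with probability 2 × C(21,8)/C(42,8) = 0.3%, and 95.5% of trials end at 19/15 or closer.

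**Step 4: how often the period test misses a 2-point effect.** At 21/13: 41% (s = 5), 66% (s = 7.07), 80% (s = 10).

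**Step 5: simulation with no treatment effect** (200,000 trials per cell, 2-point period effect). Bias is given in size and averaged over both branches. Coverage is for the paired interval when the period test is negative. Ranges at 21/13 cover both directions of imbalance.

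| s | Split | Two-step type I error | Bias | Coverage after negative test |
|---|---|---|---|---|
| 5 | 17/17 | 4.9% | 0 | 96% |
| 5 | 19/15 | 5.1% | 0.06 | 95% |
| 5 | 21/13 | 6.0% | 0.11 | 93% |
| 7.07 | 17/17 | 4.9% | 0 | 96% |
| 7.07 | 19/15 | 5.3% | 0.10 | 95% |
| 7.07 | 21/13 | 5.9–6.0% | 0.20–0.21 | 94% |
| 10 | 17/17 | 4.9% | 0 | 95% |
| 10 | 19/15 | 5.2% | 0.13 | 95% |
| 10 | 21/13 | 5.7–5.8% | 0.27 | 94.5% |

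Over period effects of 1 to 4 points, the largest two-step type I error in any of these splits is 6.0% and the largest overall bias is 0.28 point. With period always in the model, type I error is 4.9% to 5.1% in every cell.

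**Step 6: cost of always adjusting.** The standard error ratio to the paired analysis is √[(34/4)(1/n1 + 1/n2)]: 1.000 at 17/17, 1.007 at 19/15 and 1.029 at 21/13. For a true 2-point effect with s = 5 and no period effect, power is 62% for the paired t-test, 62% adjusted at 17/17 and 59% adjusted at 21/13. For the planned 5-point effect with s = 10, it is 80.8% paired, and 80.7%, 80.2% and 78.5% adjusted at 17/17, 19/15 and 21/13.

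**The case against.** The stated analysis is already a linear model with period, and the simplifying sentence is only permissive. That is true, but permission without a criterion leaves the choice of primary analysis to be made after the data are seen.

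The size is modest, and this stands. Against a 5-point target, an overall bias of at most 0.28 point and a type I error of 6% are small. They also need a real period effect together with the most lopsided loss that the planned numbers allow.

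A reader might infer much larger harm, since the same assumptions with s = 5 give a type I error of 7.5% at 23/11 and 10.9% at 25/9. The documents do not support using those figures. From 21/21 no sequence can finish with 23 or 25 patients. Such splits need unequal randomisation. The allocation method is not described, so they cannot be ruled out, but they are not the planned design.

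A reader might also infer that marked imbalance is likely. Only failure on optimal drainage removes a later suboptimal period, entrants must have improved after a lumbar tap, no failure rate on optimal drainage is given, and the 20% dropout is not described as differing by sequence. Imbalance is possible; the documents do not show it to be likely.

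**Conclusion.** The point holds as an inexpensive improvement to the analysis wording. The period test should not select the primary analysis, because missing a period effect is common (about 40% to 80% of trials for a 2-point effect) and the plan gains almost nothing by dropping the term. Within the planned numbers the consequence is limited: no harm at equal sequences, negligible inflation at 19/15, and at 21/13 the 6% type I error and 0.1 to 0.3 point overall bias shown above. These sizes rest on an assumed 2-point period effect, an assumed 0.05 period test, and three readings of the SD.

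It would be tempting to conclude that the period-adjusted model is unbiased whatever happens. The documents do not support that. A patient lost to the suboptimal period after failing on optimal drainage is lost for a reason tied to outcome, and the completers are then a selected group with or without a period term. Nor does a period term protect against carryover that differs between sequences. The simulation assumes that neither occurs.

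**What to change.** Delete the sentence in section 7c that allows the simplification. State that the primary analysis is always the linear model with treatment and period as fixed effects and patient as the within-subject unit (equivalently, a two-sample t-test comparing period differences between the sequences), whatever the period test shows. Report the period estimate with its interval as a description only.

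The change is to wording. It costs one degree of freedom at balance and, if the sequences end at 21/13, a standard error about 3% larger. N = 34 needs no change if the sequences end equal or nearly so. Outcome-related loss and unequal carryover need their own handling; this change does not address them.
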